5.2 Treatment Regimen

40 subjects with HFpEF will be administered their first dose of Entresto™ at Visit 1. Sitting systolic and diastolic BP will be monitored in the subject's dominant arm 3 times with an automatic blood-pressure monitor (Omron, Bannockburn, IL) and an average reading of these 3 measurements will be used. BPs will be checked 60 minutes after first dose is administered at Visit 1 to ensure tolerance of the medication. If tolerated, subjects will receive Entresto™ at a recommended dose of 49/51 mg on an empty stomach twice daily for up to 5 weeks. Patients will be reassessed at Visit 2 in the 5th week.

5.3 Method for Assigning Subjects to Treatment Groups

This single arm study will be performed at in the Clinical Research and Trials Unit (CRTU) at the Center for Clinical and Translational Science (CCaTS), Mayo Clinic. Subjects with circulating NEP levels of ≤ 1.55 ng/ml will be considered as having low NEP levels and those with values >1.55 ng/ml will fall into the high NEP level group

5.4 Preparation and Administration of Entresto™

- Dispensed by the Research Pharmacy
- Entresto will be taken by mouth by the patient twice daily for up to 5 weeks

5.5 Subject Compliance Monitoring

For this protocol, first dose of Entresto™ is administered in the CRTU by CRTU staff. Subsequent compliance will be monitored by a 2 week phone call made by the study coordinator.

5.6 Prior and Concomitant Therapy

Subjects should be treated with standard HF strategies (diuretics for congestion, blood pressure control and heart rate control if subject is in atrial fibrillation) as per recommended guidelines. Subjects may not take ARBs, ACE inhibitors and direct renin inhibitors during the study. If subjects are on ACEi or ARBs, these drugs will be withheld 36 hours before the initiation of treatment with Entresto™ at Visit 1. All other medications will be allowed.

5.7 Masking/Blinding of Study Drug

There is no masking or blinding of study drug since this is an open label study.

5.8 Receiving, Storage, Dispensing and Return

Will be managed by Research Pharmacy.

5.9 Receipt of Drug Supplies

Will be managed by Research Pharmacy

5.10 Storage

Entresto™ will be kept in a secure, limited-access storage area by Research Pharmacy.

5.11 Dispensing of Entresto™

Entresto™ reconciliation will be performed by the Research Pharmacy per their standard procedures.

5.12 Return or Destruction of Entresto™

Patients will be asked to destroy any unused Entresto™ tablets.

6 Study Procedures

6.1 Screening Visit

Possible study participants will meet with study coordinator to review consent form. Medical history and current medications will be reviewed. Blood will be drawn for baseline serum NEP levels, safety laboratory tests (potassium, creatinine) and pregnancy test if necessary at the CRTU. Dependent on the results of the NEP levels which will be available within 48 hours, subjects will be assigned to a high or low NEP group. If subjects are found to be eligible and are on ACEi or ARBs, subjects will be instructed to withhold these drugs 36 hours before the initiation of treatment with Entresto™ at Visit 1 and throughout the duration of the study while subjects are on Entresto™.

6.2 Visit 1

Visit 1 will occur within 30 days of the Screening Visit. Qualified subjects will be evaluated as outpatients at the CRTU. Interim history, a review of medications, NYHA class assessment and a brief physical exam will be performed by a qualified study team member. Blood will be drawn for serum NEP levels, NT-proANP, NT-proBNP, NT-proCNP, cGMP and a pregnancy test will be performed, if necessary; urine sample will also be collected for cGMP levels. An additional 55 mL blood sample will be collected from subjects, for future transcriptomic, metabolomic and genomic analysis, who provide consent to allow their blood to be stored in the BAP laboratory for future studies. Subjects will be given the option to opt in or out of this component of the study. Following this, subjects will receive their first dose of Entresto™. BPs will be monitored at baseline prior to

administration of Entresto™ and 60 minutes after this first dose to ensure tolerance of the medication. Sitting systolic and diastolic BP will be monitored in the subject's dominant arm 3 times with an automatic blood-pressure monitor (Omron, Bannockburn, IL) and an average reading of these 3 measurements will be used. Before dismissal, subjects will be provided with Entresto™ tablets for the duration of the study. Study coordinator will follow-up with the subject by telephone on day 14 ± 5 post-visit 1 to monitor compliance and to assess tolerance.

6.3 Visit 2

Upon completion of 4 weeks of drug intervention, during the 5th week of therapy subjects will be admitted as outpatients to the CRTU. Subjects will be asked to take their last dose of Entresto™ prior to their clinical visit. Interim history, a review of medications, NYHA class assessment and a brief physical exam will be performed by a qualified study team member. Baseline sitting systolic and diastolic BP will be monitored in the subject's dominant arm 3 times with an automatic blood-pressure monitor (Omron, Bannockburn, IL) and an average reading of these 3 measurements will be used. Blood will be drawn for serum NEP levels, NT-proANP, NT-proBNP, NT-proCNP and cGMP; urine sample will also be collected for cGMP levels. An additional 55 mL blood sample will also be collected from subjects, for future transcriptomic, metabolomic and genomic analysis, who provide consent to allow their blood to be stored in the BAP laboratory for future studies as in Visit 1.

7 Potential Risks and Adequacy of Protection against Risks

Protections for human subjects of research are required under Department of Health and Human Services (HHS) regulations at 21 CFR parts 50, 56, and 312.

Schedule of Events Table

Study Activity	Screen	Visit 1 Day 1	Interim Call Day 14±5	Visit 2 Week 5
Study Agent		X		X
Informed consent	X			
History (NYHA Class)	X	X	X	X
Concurrent meds	X	X	X	X
Physical Exam (Ht, Wt, BSA, VS,		X		X
Blood draw	X ^a	X ^b		X ^b
B-hCG	X ^c	X ^c		
Urine collection		X ^d		X ^d

a: Plasma NEP, serum potassium, creatinine if required

- b: Plasma NEP, NT pro-ANP, -BNP, -CNP, and cGMP; Blood for future studies
- c: Serum pregnancy test (women of childbearing potential)
- d. cGMP levels in urine sample

7 Statistical Plan

7.1 Sample Size Determination

The sample size calculation and statistical analysis have been designed in collaboration with the Division of Biostatistics. This is a proof of concept study; 40 subjects will be recruited, with 20 in each group (Group 1: subjects with HFpEF - low NEP levels and, Group 2: subjects with HFpEF - high NEP levels). It is anticipated that 100 subjects will be screened.

7.2 Statistical Methods

The primary analysis for this study will be a comparison of the changes in values of parameters of interest between the study groups low NEP vs. high NEP following up to 5 weeks of study drug intervention. This analysis will be completed using a paired t-test comparing the change from baseline to 5 weeks after study drug intervention. A secondary analysis will also be performed to evaluate the effects of the varying doses (in case, if the dose of the drug is changed during the course of the study). Analysis of variance methods will be used to compare changes from baseline to 6 hours, and pairwise group comparisons will be made via two-sample t-test if the overall ANOVA F-test is found to be significant. Distributions of changes will be examined and appropriate transformations applied prior to analyses, if necessary. Values will be expressed as the mean \pm SEM. A statistically significant difference will be considered to be present when $p < 0.05$.

8 Participant Safety and Adverse Events

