14 PUBLICATION PLAN21
15 REFERENCES.....21

List of Abbreviations

ACEIs	Angiotensin converting enzyme inhibitors
AE	Adverse Event/Adverse Experience
ANP	Atrial natriuretic peptide
ARB	Angiotensin receptor blocker
BNP	Brain natriuretic peptide
CCaTS	Center for Clinical and Translational Science
CFR	Code of Federal Regulations
cGMP	Cyclic guanosine monophosphate
CHF	Congestive Heart Failure
CNP	c-type natriuretic peptide
CRF	Case Report Form
CRTU	Clinical Research and Trials Unit
DSMB	Data and Safety Monitoring Board
EF	Ejection Fraction
ES	Executive Secretary
FDA	Food and Drug Administration
GFR	Glomerular Filtration Rate
GCP	Good Clinical Practice
HF	Heart Failure
HFrEF	Heart Failure with Preserved Ejection Fraction
HFrEF	Heart Failure with Reduced Ejection Fraction
HIPAA	Health Insurance Portability and Accountability Act
HR	Hazard ratio
IB	Investigator's Brochure
IRB	Institutional Review Board
IV	Intravenous
LVEF	Left ventricular ejection fraction
NEP	Neprilysin
NEPi	Neprilysin inhibitor
NP	Natriuretic peptide
NPRC	Natriuretic peptide clearance receptor
NYHA	New York Heart Association

Study Summary

Title	A Proof of Concept Study to Determine the Efficacy of Entresto™ in heart failure with preserved ejection fraction (HFpEF) Based on Circulating Neprilysin Levels: The Circulating NEP and NEPi (CNEPi) Study
Running Title	CNEPi
Protocol Number	IRB # 18-000044
Phase	Phase 4
Methodology	Proof of Concept Study
Overall Study Duration	21 months
Subject Participation Duration	5 weeks
Single or Multi-Site	Mayo Clinic Sites
Objectives	Determine biomarker (plasma NT-proANP, NT-proBNP, NT-proCNP, cGMP) responses to Entresto™ in patients with HFpEF who have high and low serum NEP levels
Number of Subjects	40
Diagnosis and Main Inclusion Criteria	Subjects with NYHA 2-4 HFpEF
Study Product, Dose, Route, Regimen	Entresto™ 49/51 mg (sacubitril/valsartan) orally twice-daily
Duration of Administration	Up to 5 weeks
Reference therapy	NA
Statistical Methodology	Paired t-test comparing the change from baseline to up to 5 weeks after administration of Entresto™

1 Introduction

This document is a protocol for a human research study. This study will be carried out in accordance with the applicable United States government regulations and Mayo Clinic research policies and procedures.

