1.2 Preliminary Data

Entresto™, a crystalline complex of a NEPi (sacubitril) and an angiotensin receptor blocker (ARB, valsartan), was recently approved to treat NYHA Class 2-4 patients with HFpEF after the PARADIGM-HF trial was stopped early due to an overwhelming benefit of the drug in reducing all-cause mortality (hazard ratio [HR]: 0.84; p<0.001), CV mortality (HR 0.80; p<0.001), hospitalization for HF (HR 0.79; p<0.001) and in addition reduced the symptoms and physical limitations of HF by 21% (p=0.001)¹⁵. Entresto™ due to its additional NEPi activity could be a promising new therapy for HFpEF. Entresto™ when administered to patients with HFpEF in a phase 2 study resulted in significantly reduced NT-proBNP levels, a surrogate marker of LV wall stress and NEP activity, as compared to being treated with valsartan alone¹⁶. Entresto™ therefore is being tested as treatment for HFpEF in a Phase 3 trial, PARAGON-HF, evaluating its efficacy in reducing CV death and HF hospitalizations as compared to valsartan.

NEP is a cell membrane bound metalloendopeptidase and can be released from the cell surface, resulting in the formation of a circulating peptide that maintains its catalytic activity^{17, 18}. In recent clinical studies, circulating NEP levels were significantly associated with the composite endpoint of cardiovascular death or HF hospitalization (HR 1.17; p=0.001) and cardiovascular death (HR: 1.19; p=0.002) in patients with HF¹⁹. The PARAGON-HF trial includes all-comers with HFpEF; the final data collection will be completed May 2019. It is being increasingly recognized that HFpEF is a disease entity that has considerable phenotypic heterogeneity^{20, 21}. Therefore, targeting all-comers who suffer from a heterogeneous disease process using a single treatment intervention may not result in desirable outcomes as has been evident with multiple prior negative HFpEF trials^{22, 23}. The importance of biomarker based clinical trials that deliver the right drug to the right patient is being increasingly recognized as a useful strategy to limit sample size and decrease costs by enriching such trials with potential responders^{24, 25}. Whether the beneficial effects of Entresto™ therapy are dependent on baseline NEP levels is unknown and is being explored in this study. The **hypothesis** in this proof of concept study is that

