subjects with lower NEP levels will not have an equivalent response to Entresto™, a NEPi, as compared to those with higher NEP levels. The **primary endpoint** measured is change in biomarkers with Entresto™ administration that reflect NEP activity and myocardial stress (NT pro-ANP, -BNP, -CNP) and drug action (cGMP). This endpoint has been well validated as a measure of Entresto™ drug response²⁶.

To establish a median value which will be used to categorize subjects recruited for this pilot study into a low and high NEP group we have measured circulating NEP levels in 242 samples from the **RELAX** and **NEAT-HFpEF** studies. The **RELAX study** was a multicenter, double-blind, placebo-controlled, randomized clinical trial of 216 stable outpatients with HFpEF²⁷. **NEAT-HFpEF** was a multicenter, randomized study of 110 outpatients with HFpEF²⁸. The median circulating NEP level in these populations was 1.55 ng/ml (Q1=0.49, Q3=24.99). Therefore subjects with circulating NEP levels of ≤ 1.55 ng/ml will be considered as having low NEP levels and those with values > 1.55 ng/ml will fall into the high NEP level group.

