3.1 General Design

Study design: This is a proof of concept single arm study that will be performed in the Clinical Research and Trials Unit (CRTU) at the Center for Clinical and Translational Science (CCaTS), Mayo Clinic. 40 subjects with HFpEF will be assigned to Entresto 49/51 mg (sacubitril/valsartan) twice-daily for a total duration of up to 5 weeks of treatment.

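### Section 7.2 defines a low- versus high-NEP comparison as primary but assigns it to a paired t-test, which cannot test a difference between two groups of different people

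*Combined protocol and SAP*

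**What the plan says.** The hypothesis in section 1.2 is about a difference between groups: "subjects with lower NEP levels will not have an equivalent response to Entresto™", compared with subjects who have higher levels. Section 5.3 splits subjects at 1.55 ng/ml, and section 7.1 plans 20 in each group.

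Section 7.2 sets the primary analysis to match, as "a comparison of the changes in values of parameters of interest between the study groups low NEP vs. high NEP". The next sentence names the method: "This analysis will be completed using a paired t-test comparing the change from baseline to 5 weeks after study drug intervention". The Study Summary gives the same method, with no between-group test beside it: "Paired t-test comparing the change from baseline to up to 5 weeks after administration of Entresto™".

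A two-sample test appears later in 7.2, after a sentence on a secondary analysis of varying doses. There an ANOVA is planned for the change at a 6-hour time point. The plan for its follow-up reads: "pairwise group comparisons will be made via two-sample t-test if the overall ANOVA F-test is found to be significant".

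On background treatment, section 3.1 says "This is a proof of concept single arm study". Section 4.1 asks for 30 days of stable therapy but does not require or forbid ACE inhibitor or ARB use at entry. Section 5.6 adds: "If subjects are on ACEi or ARBs, these drugs will be withheld 36 hours before the initiation of treatment with Entresto™ at Visit 1". Section 1.2 describes the study drug as containing valsartan, an ARB. Section 7.2 names no covariate.

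**The concern.** The estimand and the test in 7.2 do not match. The low- and high-NEP groups are different people, so there are no pairs across groups. A paired t-test can only ask whether the mean change from baseline is zero, within one group or over all 40 subjects. Neither answer says whether response depends on NEP level.

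The practical risk is a familiar misreading. Paired tests are run in each group, one reaches p < 0.05 and the other does not, and this is reported as a difference in response by NEP level. That pattern is common when the two groups respond identically. As written, the plan also yields no estimate or interval for the between-group difference, so a reader could not correct the misreading.

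**Working it through.** **Step 1. Can any reading of the named test give the primary comparison?**

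- *Paired test within each NEP group:* tests whether that group's mean change is zero. No contrast between groups.
- *Paired test over all 40:* tests whether the overall mean change is zero. NEP group does not enter.
- *Pairing a low-NEP with a high-NEP subject:* no matching is described anywhere.

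**Step 2. Does the two-sample test in 7.2 fill the gap?** It is tied to a change at 6 hours. Sections 6.2 and 6.3 and the Schedule of Events give biomarker draws at Visit 1, before the first dose, and at Visit 2 in week 5. The only timed post-dose measurement at Visit 1 is blood pressure at 60 minutes. There are no 6-hour data. Also, with two groups the ANOVA F statistic is the square of the two-sample t statistic, so an overall F-test followed by pairwise tests has a purpose only with three or more groups. The sentence may belong to the dose analysis or be left over from another design. In neither case does it supply the week-5 primary test.

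**Step 3. The plan's own figure.** Section 7.1 gives 20 per group with no effect size, SD or power, so 40 cannot be reproduced. Solving backwards for a two-sample t-test (two-sided 0.05, 38 df), 20 per group gives 80% power for a difference of 0.909 SD of the change. The 95% half-width is t(0.975, 38) × √(2/20) = 2.024 × 0.316 = 0.640 SD.

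**Step 4. Separate paired tests when the groups respond equally.** The documents give no change or SD, so the true change d, in SD of the change, is assumed and varied. The power p of a paired test in 20 subjects comes from the noncentral t with 19 df, noncentrality d√20 and critical value 2.093. The chance that exactly one of two independent tests is significant is 2p(1 − p).

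| d in both groups | d√20 | p | 2p(1 − p) |
|---|---|---|---|
| 0.5 | 2.236 | 0.5645 | 2 × 0.5645 × 0.4355 = 0.492 |
| 0.7 | 3.130 | 0.8435 | 2 × 0.8435 × 0.1565 = 0.264 |
| 1.0 | 4.472 | 0.9886 | 2 × 0.9886 × 0.0114 = 0.023 |

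The true group difference is zero in every row, and a two-sample test rejects in 5%.

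**Step 5. Pooled paired test.** With d = 0.5 in all 40 subjects, the noncentrality is 0.5 × √40 = 3.162, with 39 df and critical value 2.023. It rejects with probability 0.87, although the groups do not differ.

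**Step 6. Prior ACEi/ARB use, on assumed values only.** Let prior users and non-users differ by k in mean change (in residual SD), and let the realised share of users differ by g between NEP groups. The unadjusted contrast is then shifted by g × k:

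- g = 0.20, k = 0.5 to 1.0: shift 0.10 to 0.20 SD. Simulated false-positive rate of the two-sample test about 5.5% to 6%.
- g = 0.40, k = 0.5 to 1.0: shift 0.20 to 0.40 SD. Rate about 8.5% to 18%.
- g = 0: no shift.

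A model with NEP group and prior use holds about 5% if prior use is the only confounder. Its half-width is t(0.975, 37) × √(0.1/(1 − g²)) = 0.641, 0.654 or 0.699 SD at g = 0, 0.2 or 0.4.

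**The case against.** The strongest defence is that the authors meant a two-sample test. The first sentence of the analysis is plainly between-group, a two-sample t-test is named in the same paragraph, and transformation of skewed changes is already foreseen. This makes a drafting slip more likely than a mistaken method, and it stands as a reading of intent. It does not repair the text: the method sentence and the Study Summary both say paired, and the two-sample test is tied to a time point that is never sampled.

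A reader might go further and infer that the unadjusted comparison is confounded by prior ACEi/ARB use. The groups are not randomised, and the visit-to-visit change means a newly started ARB plus NEP inhibition in non-users but replaced or resumed blockade plus NEP inhibition in prior users. The documents do not support that inference. Nothing in them links prior use to NEP level, and nothing says how far prior use shifts these biomarkers. The valsartan comparison cited in section 1.2 concerns NT-proBNP only. The 36-hour withholding rule also makes drug status at baseline more uniform, though it does not erase the difference in history. Whether NEP level marks responders is itself an unadjusted question, so an unadjusted primary contrast is defensible.

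**Conclusion.** The mismatch is certain from the text: as written, the named primary test does not address the stated primary comparison or the hypothesis. Its consequence depends on the true change, which the documents do not give. With equal true changes of 0.5 to 1.0 SD and 20 per group, discordant paired results arise in 49% down to 2% of trials. These are not type I error rates of a between-group test. They show how often a mistaken inference would be invited.

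The point on prior ACEi/ARB use is secondary. Confounding is possible but not shown, and its size and direction cannot be computed from the documents. It justifies a description and a sensitivity analysis. It does not support a finding that the plan is biased.

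**What to change.** **Primary analysis (section 7.2 and Study Summary).** Suggested wording: *For each biomarker, the change from Visit 1 to Visit 2, log-transformed where needed, will be compared between the low- and high-NEP groups by a two-sample t-test and reported as the difference with its 95% confidence interval. Paired t-tests describe change within each group only and are not used to infer a difference between groups.* Delete the 6-hour ANOVA sentence, or reconcile it with the visit schedule and say which analysis it serves. This costs wording only, with no added subjects, samples or visits.

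**Sensitivity analysis, optional.** Tabulate ACEi/ARB use at screening by NEP group, taken from the medication review in section 6.1 and the Schedule of Events, because users are off these drugs by Visit 1. Beside the primary contrast, report a linear model of change on NEP group plus prior ACEi/ARB use (yes/no). Give confidence intervals only, so that the four adjusted estimates are not a second route to a significance claim. Section 8.10 shows that this text was written after the study began, so label the model post hoc if outcome data have been seen.

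The adjusted model costs one degree of freedom (37 instead of 38) and a slightly wider interval: half-width 0.641 to 0.699 SD against 0.640 for gaps of 0 to 40 points, if prior use does not affect the change. Adjusting for one factor can also worsen bias. If prior use shifts the contrast by +0.20 SD and an unmeasured factor by −0.20 SD, the unadjusted bias is zero, and adjusting for prior use alone leaves −0.20 SD. Both estimates should therefore be shown. No change to the withholding rule is proposed.

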1.3 Dose Rationale and Risk/Benefits

The effect of administering Entresto™ to subjects with “high” or “low” NEP levels will be studied. Favorable response to Entresto™ therapy in these subjects will be assessed by evaluating a change in biomarkers that reflect NEP activity, myocardial wall stress and clinical outcomes (NT-proANP, NT-proBNP, NT-proCNP)²⁹ and reflect efficacy of drug action (cGMP)²⁶. Entresto is FDA approved for use in HFrEF and will be administered as recommended in the drug labeling information as an off label use in HFpEF as 49/51 mg twice-daily.

2 Study Objectives

Primary Objective: To determine biomarker (plasma NT-proANP, NT-proBNP, NT-proCNP and cGMP) responses to Entresto™ in patients with HFpEF who have high and low serum NEP levels.

3 Study Design

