4.6 Data Collection and Follow-up for Withdrawn Subjects

[figure not shown]
Subjects will complete all study assessments of Study Visit 2 if they have received study drug for at least 2 weeks or more, regardless of whether they have received the full 5 weeks of study drug treatment. The blood collection component of the study assessment will need to occur within 24 hours of drug discontinuation.

5 Study Intervention

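### The primary comparison is low NEP versus high NEP, but the test named for it is a paired t-test of change over time, which gives no low-versus-high result

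*Combined protocol and SAP*

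**What the plan says.** Section 7.2 (Statistical Methods) describes the primary analysis as "a comparison of the changes in values of parameters of interest between the study groups low NEP vs. high NEP" after the treatment period. The sentence that follows assigns the method: "This analysis will be completed using a paired t-test comparing the change from baseline to 5 weeks after study drug intervention". The Study Summary, under Statistical Methodology, gives only "Paired t-test comparing the change from baseline to up to 5 weeks after administration of Entresto™" and mentions no comparison of groups.

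The hypothesis in Section 1.2 is between groups: "subjects with lower NEP levels will not have an equivalent response to Entresto™, a NEPi, as compared to those with higher NEP levels". The objective in Section 2 is looser, namely biomarker "responses to Entresto™ in patients with HFpEF who have high and low serum NEP levels", and can be read as describing each group.

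The groups are formed by a cut-off. Under Section 5.3, subjects at or below 1.55 ng/ml "will be considered as having low NEP levels and those with values >1.55 ng/ml will fall into the high NEP level group". Section 7.1 gives the numbers: "40 subjects will be recruited, with 20 in each group". No matching of subjects across groups is described.

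Section 7.2 also mentions a secondary analysis by dose. It then gives an ANOVA of changes from baseline to 6 hours, with two-sample t-tests to follow if the F-test is significant. On timing, Section 4.6 states: "Subjects will complete all study assessments of Study Visit 2 if they have received study drug for at least 2 weeks or more", whether or not they completed 5 weeks.

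**The concern.** A paired t-test needs two measurements that belong together. Here those are one subject's baseline and Visit 2 values, so the test answers whether the mean change is zero. Nothing links a low-NEP subject to a particular high-NEP subject, so the test cannot be applied across the groups.

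The contrast the study exists to examine is therefore declared primary without a method that yields it. Followed as written, the method gives one or two statements about change from baseline and none about whether the change depends on NEP level. An analyst would have to substitute another test without a written rule. Two analysts could then report different primary results from the same data. One could also be tempted to infer a group difference because the change is significant in one group and not in the other, which is not a valid comparison.

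**Working it through.** **1. Does another sentence supply the between-group test?** The only two-sample t-test is in the ANOVA sentence of Section 7.2. It does not serve the primary analysis, for three reasons:
- It follows the secondary dose analysis, and the text does not say whether its groups are NEP groups or dose groups.
- It depends on a significant F-test.
- It concerns change to 6 hours. Biomarker blood is drawn only at Visits 1 and 2 (Sections 5.1, 6.2 and 6.3 and the Schedule of Events), and Section 12.2 gives weeks 0 and 5. The only scheduled measurement soon after the first dose is blood pressure at 60 minutes.

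**2. Is there a planned figure to reproduce?** No. Section 7.1 gives 20 per group without effect size, SD, power or dropout. Everything below is in units of the SD of the change score, with significance level 0.05 (Section 7.2). Two-sided testing is assumed because sidedness is not stated.

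**3. Sensitivity of each test at 80% power, by the noncentral t distribution.**
- Paired test: df = n − 1, noncentrality d√n.
- Two-sample test on changes: df = 2n − 2, noncentrality d√(n/2).

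| Test | Question | Detectable effect |
|---|---|---|
| Paired, one group, n = 20 | mean change versus zero | 0.660 SD |
| Paired, pooled, n = 40 | mean change versus zero | 0.454 SD |
| Two-sample, 20 per group | low versus high | 0.909 SD |
| Two-sample, 18 per group (assumed) | low versus high | 0.961 SD |
| Two-sample, 16 per group (assumed) | low versus high | 1.024 SD |

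The last two rows show the effect of leaving out early Visit 2 draws on a strict reading of 5 weeks; the counts are assumptions.

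The 95% CI half-width for the difference, with 20 per group, is t(0.975, 38) × √(2/20) = 2.024 × 0.316 = 0.640 SD.

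**4. Illustration: what if paired tests were used to judge the groups?** The plan states no such rule, and the effect sizes are assumed. Suppose both groups truly change by the same d, and each has a paired test with n = 20 and power p. The chance that exactly one is significant is 2p(1 − p).

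| Common change d | p | 2p(1 − p) | Simulated | Welch test rejects |
|---|---|---|---|---|
| 0.3 SD | 0.2471 | 0.372 | 0.372 | 0.049 |
| 0.45 SD | 0.4803 | 0.499 | 0.498 | 0.050 |
| 0.8 SD | 0.9239 | 0.141 | 0.139 | 0.049 |
| 1.0 SD | 0.9886 | 0.023 | 0.023 | 0.050 |

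The simulations used 200,000 trials per setting. A pooled paired test (n = 40) does no better as evidence about groups: with a common change of 0.5 SD it is significant 87% of the time although the groups do not differ.

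**The case against.** The strongest reply is that this is a mislabelled test and not a missing contrast. The first sentence of Section 7.2 states the comparison plainly, the hypothesis and the 20/20 grouping agree with it, and any statistician would produce a two-sample test on the changes. That is a fair reading of intent. On that reading the error rate is 5% for each biomarker and only the name is wrong. But the same paragraph uses the term two-sample t-test elsewhere, so paired cannot safely be taken as shorthand for it. The Study Summary repeats the paired test alone, and the Section 2 objective makes a within-group reading plausible.

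Other points stand in part:
- The plan does not say whether paired tests would be run by group or pooled, so 0.66 SD is one reading and 0.45 SD the other.
- The percentages in step 4 rest on a rule that the plan does not contain.
- Most of the text speaks of up to 5 weeks, and with Section 4.6 that favours including early Visit 2 draws. The 18- and 16-per-group rows are only a bound.
- Welch is one acceptable choice. A baseline-adjusted ANCOVA would also give the contrast.

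None of these supplies a between-group test for the Visit 2 change.

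**Conclusion.** The concern holds and should be corrected before analysis. The named test does not match the declared primary comparison, and this follows from the text without any assumption about effect size or SD.

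The figures describe the gap; they are not the ground for the finding. With 20 per group the smallest low-versus-high difference detectable at 80% power is 0.91 SD of change, against 0.66 SD for a change from zero within one group. They assume two-sided 0.05 for a single biomarker, normally distributed changes and equal SDs. Judging the groups by separate paired tests would give discordant results in 2% to 50% of trials over the assumed common changes of 0.3 to 1.0 SD, when no difference exists. The time-point inconsistency is real but secondary.

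**What to change.** In Section 7.2 and the Study Summary:
1. Name the primary test for each biomarker: a two-sample (Welch) t-test, low versus high NEP, on each subject's Visit 1 to Visit 2 change. Report the difference with its 95% CI.
2. State that the early Visit 2 draws allowed by Section 4.6 are included, and use one description of the time point throughout.
3. Fix the analysis scale in advance. Any log transformation should be applied to the measured values before the change is formed, because a negative change has no logarithm.
4. Keep paired t-tests as within-group description for the Section 2 objective.
5. Reconcile the ANOVA sentence with the visit schedule: either replace 6 hours with Visit 2 and say that it concerns the secondary dose groups, or delete it.

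The cost is a wording amendment. Sections 8.1 and 11.2 exempt only administrative changes from IRB approval, and a change to the primary test is best treated as needing it. Section 8.10 mentions a decision taken during the study, so the amendment should be dated and should state whether outcome data had been examined. No new data, visits or patients are needed. Whether 20 per group is enough is a separate question, because the documents give no target effect.
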